9.4.2 Safety endpoints

For all safety analyses, the safety set will be used. All listings, figures and tables will be presented by treatment group.

Adverse events

All information obtained on adverse events will be displayed by treatment group.

The number (and percentage) of participants with treatment emergent adverse events (events started after the first dose of study medication or events present prior to start of double-blind treatment but increased in severity based on preferred term) will be summarized in the following ways:

- by treatment, primary system organ class and preferred term.
- by treatment, primary system organ class, preferred term and maximum severity.
- by treatment, Standardized Medical Dictionary for Regulatory Activities (MedDRA) Query (SMQ) and preferred term.

Separate summaries will be provided for study medication related adverse events, death, serious adverse events, other significant adverse events leading to discontinuation, and adverse events leading to dose adjustment.

The number (and proportion) of participants with adverse events of special interest and related to potential risks (as per the Investigator's Brochure) will be summarized by treatment.

A participant with multiple adverse events within a primary system organ class is only counted once towards the total of the primary system organ class.

Adverse events which will be counted for a specific treatment period are those which are treatment-emergent. These events are those with an onset after the start of the treatment period, or which were present prior to the start of the treatment period but increased in severity, changed from being not suspected to being suspected of study treatment relationship, or developed into SAEs after the start of the treatment period.

More details on the analysis of AE will be described in the Statistical Analysis Plan (SAP).

Vital signs

Summary statistics will be provided by treatment and visit for all vital signs, as well as for the proportion of participants presenting with clinically notable abnormal values. Graphical displays of the values of selected vital signs over time may be provided by treatment group.

More details on the analysis of vital signs will be described in the Statistical Analysis Plan (SAP).

12-lead ECG

A standard 12 lead ECG will be performed at Visit 1, visit 30, visit 170 and visit 1999. Interpretation of the tracing must be made by a qualified physician and documented on the ECG section of the CRF. Each ECG tracing should be labeled with the study and subject number, date, and kept in the source documents at the study site. Clinically significant abnormalities

should also be recorded on the Medical History/AE CRF page. Summary statistics for continuous data and number and percentage of participants for categorical data (e.g. interpretation) will be provided by treatment and visit.

More details on the analysis of ECG parameters will be described in the SAP.

[figure not shown]
Clinical laboratory evaluations

Laboratory data collected during the study will be summarized by presenting shift tables using extended normal ranges (baseline to most extreme post-baseline value), summary statistics of raw data and change from baseline. The number of participants meeting pre-defined clinically notably laboratory values and percent changes will also be summarized.

[figure not shown]
For the rate change in eGFR, the eGFR slope will be estimated from a repeated measures ANCOVA model including treatment, number of background antihypertensive medications (3 or >3), region, time (when the eGFR is assessed in weeks), and treatment-by-time as fixed effects with random intercept and slope (time) and a common unstructured covariance. The least-square means of slopes for within and between treatment groups, and the corresponding two-sided 95% confidence intervals will be provided.

More details on the analysis of clinical laboratory parameters will be described in the SAP.

9.6 (Other) Safety analyses

Please refer to statistical analysis plan for details.

9.7 Other analyses

Subgroup analyses

The subgroups of interest for primary endpoint and selected secondary endpoints include but are not limited to:

- Age (<60, >=60 years)
- Age (<=median, > median)
- Sex (male, female)
- Region
- Number of background antihypertensive medications (3, >3)
- eGFR (<60, >=60 mL/min/1.73m²)

Please refer to statistical analysis plan for details.

9.8 Interim analysis

One interim safety analysis will be conducted when approximately first 40 participants complete at least 5 weeks of double-blind treatment. Regular safety data monitoring is planned as specified in Section 4.6. No alpha adjustment will be made for the interim safety analysis and safety data monitoring. Interim safety analysis and safety data monitoring will be performed by an independent statistician who will not be involved in the trial conduct. The results will be reviewed by the independent DMC.

The primary analysis will be performed after all participants have completed Week 12 (or discontinued prior to Week 12). A final analysis will be performed after all participants have completed Week 20 (or discontinued prior to Week 20). Formal testing of the primary endpoint with full level alpha of 0.025 (1-sided) will be performed at the primary analysis timepoint.

9.9 Sample size determination

9.9.1 Primary endpoint(s)

The study is planned to randomize 170 participants including approximately 10% lost to follow-up, allocated in the ratio of 1:1:1:1:1 to placebo, XXB750 30 mg SC q4w, 60 mg SC q4w, XXB750 120 mg SC q4w and XXB750 240 mg SC q4w, respectively.

Assuming a common standard deviation of 12 mmHg for mean 24hr SBP change from baseline and a one-sided 2.5% significance level (with adjustments for multiple comparisons using MCP-MOD), a sample size of 150 participants (30 each in placebo, XXB750 30 SC q4w, XXB750 60 mg SC q4W, and XXB750 120 mg SC q4w, and XXB750 240 mg SC q4w) will provide a minimum power of 92% if the underlying true maximum mean 24hr SBP reduction on XXB750 vs placebo is 10 mmHg.

9.9.2 Secondary endpoint(s)

Assuming a common standard deviation of 12 mmHg for mean 24hr SBP change from baseline and a one-sided 2.5% significance level, a sample size of 30 participants in placebo and in XXB750 highest dose, respectively, will provide approximately 89% power if the true mean 24hr SBP reduction on XXB750 vs placebo is 10 mmHg.

Secondly, same assumption as first secondary endpoint is used for the average change from baseline in mean 24hr SBP at Week 9 and at Week 12 and a one-sided 2.5% significance level, a sample size of 30 participants in placebo and in XXB750 highest dose, respectively, will provide approximately 89% power if the true mean 24hr SBP reduction on XXB750 vs placebo is 10 mmHg.

Lastly, assuming a one-sided 2.5% significance level (with adjustments for multiple comparisons using MCP-MOD), a sample size of 150 participants (30 each in placebo, XXB750 30 mg SC q4w, XXB750 60 mg SC q4W, XXB750 120 mg SC q4w, and in XXB750 240 mg SC q4w) will provide a minimum power of 76% if the underlying true BP control achievement in placebo and XXB750 doses range from 10% to 45%, respectively.

10 Supporting documentation and operational considerations

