- Adverse events, safety laboratory parameters, and vital signs through end of treatment/study (EOT/EOS)

and without any unforeseen increase in the dose of allowed background antihypertensive medications nor receiving any prohibited medications. It will provide an estimate with a p-value in a hierarchical hypothesis testing procedure with overall type I error control after previous primary and secondary objectives are demonstrated.

 To evaluate the safety and tolerability of the XXB750 regimens over 12 weeks of treatment and over the overall 20 weeks of study duration including safety follow-up.

Trial Design:

Study XXB750B12201 is a multicenter, randomized, double-blind, placebo-controlled, parallel-group phase 2 study which is comprised of four periods:

- A screening period (approximately 7 days)
- A single-blind placebo run-in period lasting approximately 2 weeks
- A 12-week double-blind, placebo-controlled, parallel-group treatment period
- An 8-week safety follow-up period

The study will enroll participants with rHTN defined as participants with uncontrolled BP despite treatment with optimal or maximally tolerated doses of 3 or 4 antihypertensive drugs of different classes, including a thiazide/thiazide-like diuretic, an ACEI or an ARB, and a long acting dihydropyridine CCB. Approximately 170 participants will be randomized to receive placebo, XXB750 30 mg, 60 mg, 120 mg, or 240 mg SC every 4 weeks.

Brief Summary:

XXB750 is a fully human monoclonal antibody with potent NPR1 agonistic activity. NPR1 agonism induces the effects of natriuretic peptides, enhancing Natriuresis, diuresis and vasodilatation. Consistent with its mechanism of action, XXB750 was shown to have a potent blood pressure lowering effect in healthy human volunteers. Study XXB750B12201 aims to evaluate the antihypertensive effect of XXB750 in subjects with resistant hypertension.

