3.2 Secondary estimands

Difference between highest XXB750 dose group versus placebo in change from baseline in mean 24-hour SBP at Week 12

The estimand of the first secondary objective in terms of attributes will be the same as described for the primary estimand (Section 3.1) except for the treatment of interest, which is restricted to the highest XXB750 dose group and placebo only.

This estimand will further demonstrate the efficacy of XXB750 highest dose group compared with placebo and provide an estimate with a p-value in a hierarchical hypothesis testing procedure with overall type I error control after a dose-response signal is established in the primary objective.

Difference between highest XXB750 dose group versus placebo in average of changes from baseline in mean 24-hour SBP at Week 9 and at Week 12

The estimand of the second secondary objective in terms of attributes are the same as described for the primary estimand (Section 3.1) except for (1) the treatment of interest which is restricted to the highest XXB750 dose group and placebo only; and (2) for variable which is average change from baseline in mean 24hr SBP at Week 9 and at Week 12.

This estimand will demonstrate the overall efficacy of XXB750 highest dose group compared with placebo in terms of average change from baseline at Week 9 (approximate peak state) and at Week 12 (approximate trough state) and provide an estimate with a p-value in a hierarchical hypothesis testing procedure with overall type I error control after efficacy in primary and first secondary objectives are established.

Dose-response signal and dose-response relationship of XXB750 dose groups versus placebo with respect to the proportion of participants achieving blood pressure (BP) control at Week 12

The third secondary question of interest is: What is dose-response signal and assess the dose-response relationship of XXB750 30 mg SC q4w, 60 mg SC q4w, 120 mg SC q4w, and 240 mg SC q4w versus placebo with respect to the proportion of participants achieving BP control at Week 12 in patients with rHTN without any premature discontinuation from study treatment and without any increase in the dose of allowed background antihypertensive medications nor receiving any prohibited medications.

The key secondary estimand is described by the following attributes:

- 1. Population: participants with rHTN receiving allowed concomitant medications defined in study population (Section 5).

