9.3.2 Statistical model, hypothesis, and method of analysis

The primary objective of determination of a dose-response signal and to characterize the dose-response relationship in XXB750 doses compared to placebo will be evaluated using an optimally weighted contrast test following the Multiple Comparison Procedure-Modeling (MCP-MOD) methodology described in (Pinheiro et al 2006, Pinheiro et al 2014).

A candidate model set is defined corresponding to the range of the expected mean response in each of the dose groups. The candidate model set is used to generate a set of weights for the calculation of optimal contrasts between the responses in the studied dose groups and the placebo group. A statistical test comparing all doses in the different dose groups simultaneously to the placebo is used, hence a multiplicity adjustment is applied that accounts for the multiple possible dose response behavior considered. A critical value is derived from a multivariate t-distribution using the correlation matrix induced by the correlations between the weights corresponding to the candidate sets as well as the correlation between the tests of shapes in the dosing groups to the placebo group.

Test of the dose response signal

The null hypothesis of a flat dose-response relationship for the change from baseline in mean 24-hour ambulatory systolic blood pressure (mean 24 hr SBP) compared to placebo will be tested at a 1-sided significance level of 2.5% against the alternative hypothesis of a dose-response relationship leading to a significant reduction in the mean 24 hr SBP.

Hence, the following null and alternative hypotheses will be tested:

[figure not shown]
- **H**₁₀: there is no dose-response relationship for XXB750 (i.e. all dose groups have the same response mean as the placebo group).
- **H**₁₁: there is a dose-response relationship for XXB750 (i.e. at least one dose-groups has a response mean different from the placebo group).

There are five candidate models to capture the shape of the dose-response relationship for XXB750 at Week 12 endpoint, as depicted in Figure 9-1. The candidate models generating the contrast weights are described below:

Model 1: Emax with ED50 at 30 mg SC q4w

- Model 2: Emax with ED50 at 60 mg SC q4w
- Model 3: sigmoid Emax with ED50 at 30 mg SC q4w and hill parameter h=3
- Model 4: sigmoid Emax with ED50 at 120 mg SC q4w and hill parameter h=3
- Model 5: Beta-model with delta1=0.2, delta2=0.3 and scale=288

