9.3.5 Multiplicity adjustment (if applicable)

Please refer to Section 9.3.2 for primary analysis of MCP-MOD for multiplicity adjustment with respect to testing for a dose response signal across multiple candidate shapes. The secondary hypotheses included in the order of hierarchical testing procedure are: (1) evaluate and demonstrate treatment effect of highest XXB750 dose group versus placebo in reducing the mean 24hr SBP from baseline to Week 12, (2), evaluate and demonstrate treatment effect of highest XXB750 dose group versus placebo in reducing the average of mean 24hr SBP from baseline to Week 9 and Week 12 and (3) dose-response relationship in terms of proportions of participants achieving BP control among XXB750 dose groups and placebo. The secondary hypotheses will be tested in the order described above and statistical inference will be made only if the primary hypothesis is rejected.

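### Must the 89% power for the highest-dose comparison be restated because one candidate dose-response shape would give about 71%?

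*Protocol*

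**What the plan says.** Protocol 9.9.1 takes 30 evaluable participants per arm and an SD of 12 mmHg and gives the primary dose-response test (H10) a "minimum power of 92% if the underlying true maximum mean 24hr SBP reduction on XXB750 vs placebo is 10 mmHg".

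Protocol 9.9.2 then treats the secondary tests one at a time. The first (H20, highest dose versus placebo at Week 12) opens with "Assuming a common standard deviation of 12 mmHg for mean 24hr SBP change from baseline and a one-sided 2.5% significance level", names 30 participants on placebo and 30 on the highest dose, and gives "approximately 89% power if the true mean 24hr SBP reduction on XXB750 vs placebo is 10 mmHg". The second (H30, average of Weeks 9 and 12) uses the same assumptions and result. The third (H40, dose response in BP control) has a "minimum power of 76% if the underlying true BP control achievement in placebo and XXB750 doses range from 10% to 45" per cent. SAP 3.1 and 3.2 repeat all of this.

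The candidate shapes in Protocol 9.3.2 and SAP 2.5.2 are two Emax models, two sigmoid Emax models and "Model 5: Beta-model with delta1=0.2, delta2=0.3 and scale=288".

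On the order, Protocol 9.3.5 says "The secondary hypotheses will be tested in the order described above". Protocol 3.2 places H30 "after efficacy in primary and first secondary objectives are established", and Table 1-1 puts H40 in a "hierarchical hypothesis testing procedure with overall type I error control after previous primary and secondary objectives are demonstrated".

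**The concern.** Two adjacent subsections use 10 mmHg for different quantities: the largest effect at any dose in 9.9.1, and the effect at the highest dose in 9.9.2. For a shape that turns down before 240 mg, the first does not imply the second, and the plan includes such a shape in its candidate set.

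The gap falls on H20, which controls access to H30 and H40. If H20 is weaker than a reader supposes, so is everything behind it. The 89% and 76% are also not labelled as powers of each test taken alone, so they could be read as chances of success through the whole sequence. At stake would be an over-optimistic view of how often the secondary claims can be made.

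**Working it through.** **Inputs.** SD 12 mmHg, 30 per arm and one-sided 2.5% (Protocol 9.9.1 and 9.9.2); doses 0, 30, 60, 120 and 240 mg; the five candidate models (Protocol 9.3.2).

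**1. The stated 89%.** The standard error of a two-arm difference is 12 × √(2/30) = 3.098 mmHg. At 10 mmHg the standardised effect is 10 / 3.098 = 3.227.

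- Normal approximation: Φ(3.227 − 1.960) = 89.8%.
- Noncentral t: 88.8% with 58 df, or 89.4% with 145 df (150 − 5, all five arms contributing to the variance).

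The 89% is reproduced.

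**2. The stated 92%.** I reconstructed the MCP-Mod test with optimal contrasts for equal arms, a multivariate t reference with 145 df and a simulated critical value of 2.32. With the maximum over doses set to 10 mmHg, power for Models 1 to 5 is 92.7, 91.9, 95.8, 95.5 and 93.4%. The minimum is about 92%, at Model 2, so the 92% holds with Model 5 included.

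**3. The stated 76%.** On the logit scale, with control running from 10% to 45% and large-sample variances, power for Models 1 to 5 is 81.9, 85.0, 88.2, 94.4 and 76.6%. The minimum is at Model 5 and matches the plan. A binomial simulation with estimated variances and equal-weight contrasts gives 88% or more for every model, so the 76% is reproduced by the large-sample calculation only. The plan does not describe its method. The point below does not depend on this.

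**4. Model 5 at 240 mg.** The Beta model is B × (d/288)^0.2 × (1 − d/288)^0.3, with B = 0.5^0.5 / (0.2^0.2 × 0.3^0.3) = 1.400.

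- Peak: 288 × 0.2/0.5 = 115.2 mg.
- At 240 mg: 1.400 × 0.964 × 0.584 = 0.789 of the maximum.
- With a 10 mmHg maximum, the effects at 30, 60, 120 and 240 mg are 8.62, 9.54, 10.00 and 7.89 mmHg.

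Models 1 to 4 reach their largest effect over the tested doses at 240 mg, so for them the two meanings of 10 mmHg coincide.

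**5. H20 power at 7.89 mmHg.** The standardised effect is 7.89 / 3.098 = 2.546. Power is 72.1% (normal), 70.7% (t, 58 df) or about 71.5% (t, 145 df). The chance of missing H20 goes from 11% to 29%. To recover 89% under Model 5, the maximum would have to be 10 / 0.789 = 12.7 mmHg.

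**6. Effect of the order at H20.** The chance of rejecting both H10 and H20 is about 87 to 89% under Models 1 to 4 and about 71% under Model 5. The primary test in front of H20 therefore costs little.

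**7. Sensitivity to the SD.** The plan does not say whether 12 mmHg is before or after baseline adjustment. If it is before, assumed baseline-to-change correlations of 0, 0.3 and 0.5 give residual SDs of 12.0, 11.4 and 10.4. H20 power is then 70.7, 74.7 and 82.4% for Model 5, against 88.8, 91.4 and 95.6% for Models 1 to 4.

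**8. Does 71% limit the 76%?** Only if the SBP effect behind 10% to 45% control is also a 10 mmHg maximum, and the plan does not give that effect. Taking the SBP component alone and a normal Week 12 level (my assumptions), the shift needed is 1.156 SD. Week 12 SDs of 8.65, 10 and 12 mmHg imply maxima of 10.0, 11.6 and 13.9 mmHg and Model 5 H20 powers of 70.7, 82.5 and 93.5%. A limit below 76% is possible but not established.

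**The case for a change.** The best argument for adding the scenario has three parts. First, the plan appears to allow for Model 5 elsewhere: its 76% for H40 matches the Model 5 value in step 3, and without that shape the minimum would be about 82%. H20 is then the one test in this set reported without it. Second, a downturn is not far-fetched. Week 12 is four weeks after the last dose, and Protocol 4.3 reports day-28 SBP changes of about 7 mmHg at 120 mg and about 5 mmHg at 240 mg in healthy volunteers. Third, the remedy would cost only a few sentences.

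The first part stands as a description: H20 power is given for a named effect, not as a worst case over shapes. But 9.9.2 calls the 76% a minimum and does not call the 89% one, so the text shows the difference. The second part makes the scenario reasonable, but the data are preliminary, follow a single dose and are not stated to be placebo-adjusted at day 28, so they do not settle the shape. The third part is true, but low cost is not a reason when no analysis, decision or conclusion would differ.

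**Conclusion.** No change is needed. The three stated powers are consistent with their own assumptions, and the passage giving 89% names both the comparison and the effect it assumes. Each secondary calculation is set out separately at its own one-sided 2.5% level, which a statistician will read as the power of that test alone. That a later test in a fixed sequence cannot succeed more often than an earlier one follows from the procedure, and the order is stated plainly in both documents.

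What is left is an unreported scenario: under Model 5 with a 10 mmHg maximum, H20 has about 71% power instead of 89%. This takes 30 per arm and 12 mmHg as the SD that applies in the analysis; if 12 mmHg is the unadjusted SD, the Model 5 figure lies between 71% and 82% for correlations of 0 to 0.5. It does not show that the 76% for BP control is overstated.

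The practical consequence is small. The study is a dose-finding trial sized on the dose-response signal, which keeps about 93% power under Model 5, and the Beta model is among those fitted when the curve is estimated, so a downturn can still be detected and described. Reporting the 71% would change neither the sample size, the tests, their order nor the error control.

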10.1 Appendix 1: Regulatory, ethical, and study oversight considerations

10.1.1 Regulatory and ethical considerations

This study will be conducted in accordance with the protocol and with the following:

- Consensus ethical principles derived from international guidelines including the Declaration
 of Helsinki and Council for International Organizations of Medical Sciences (CIOMS)
 international ethical guidelines
- Applicable ICH Good Clinical Practice (GCP) guidelines
- Applicable laws and regulations

The protocol, protocol amendments, ICF, Investigator's Brochure, Investigational directions for use (IDFU), and other relevant documents (e.g. advertisements) must be submitted to an IRB/IEC by the Investigator and reviewed and approved by the IRB/IEC before the study is initiated.

Any amendments to the protocol will require IRB/IEC approval before implementation of changes made to the study design, except for changes necessary to eliminate an immediate hazard to study participants.

Protocols and any substantial amendments/modifications to the protocol will require health authority approval prior to initiation except for changes necessary to eliminate an immediate hazard to study participants.

The Investigator will be responsible for the following:

Signing a protocol signature page confirming his/her agreement to conduct the study in accordance with these documents and all of the instructions and procedures found in this protocol and to give access to all relevant data and records to Novartis monitors, auditors, Novartis Quality Assurance representatives, designated agents of Novartis, IRBs/IECs, and regulatory authorities as required,

Providing written summaries of the status of the study to the IRB/IEC annually or more frequently in accordance with the requirements, policies, and procedures established by the IRB/IEC

Notifying the IRB/IEC of SAEs or other significant safety findings as required by IRB/IEC procedures.

Providing oversight of the conduct of the study at the site and adherence to requirements of 21 CFR, ICH guidelines, the IRB/IEC, European regulation 536/2014 for clinical studies (if applicable), European Medical Device Regulation 2017/745 for clinical device research (if applicable), and all other applicable local regulations

Inform Novartis immediately if an inspection of the clinical site is requested by a regulatory authority.

This clinical study was designed and shall be implemented, executed and reported in accordance with the ICH Harmonized Tripartite Guidelines for Good Clinical Practice, with applicable local regulations (including European Directive 2001/20/EC or European Clinical Trial Regulation 536/2014, US CFR 21), and with the ethical principles laid down in the Declaration of Helsinki.

